Study Protocol and Statistical Analysis Plan

A prospective open controlled study of creatine combined with curcumin in the intervention of early cachexia in upper gastrointestinal tumors.

NCT number: 05856500

Date: May 12, 2023

Nanjing Drum Tower hospital

The Affiliated Hospital of Nanjing University Medical School

Summary

Project Name	A prospective open controlled study of creatine combined with curcumin in the intervention of early cachexia in upper gastrointestinal tumors
Purpose of the study	
(1) To investigate whether creatine combined with curcumin can improve the inflammatory state, correct the disorder of nutrient metabolism and improve the nutritional status in the early cachexia stage of upper gastrointestinal neoplasms.
 
(2) To investigate whether creatine combined with curcumin can improve the quality of life and prognosis of patients with early cachexia in upper digestive tract tumors.

Study Design	The effect of creatine combined with curcumin on inflammatory state, nutritional metabolism, nutritional state and prognosis of patients with early cachexia of upper digestive tract tumors was investigated in a prospective open controlled study
Total number of cases	152 cases
Criteria	
Inclusion Criteria:
 
(1) Clinical diagnosis of advanced tumors of the upper digestive tract with untreatable or postoperative recurrence of esophageal and gastric cancer III-IV
 
(2) Meet the diagnostic criteria of early cachexia (anorexia and metabolic changes, involuntary body mass reduction $\leq 5\%$ within 6 months)
 
(3) Radiotherapy, chemotherapy, or immunotherapy in our hospital
 
(4) Understand and fill in a variety of rating scales
 
(5) Informed consent, voluntary participation in this study
 
Exclusion Criteria:
 
(1) Neoadjuvant chemotherapy patients
 
(2) Intestinal obstruction or gastrointestinal bleeding
 
(3) Severe heart, lung and renal insufficiency
 
(4) Coagulopathy
 
(5) Clinical diagnosis with diabetes and other metabolic diseases
 
(6) The expected survival time is less than 1 month
 
(7) With cognitive dysfunction or poor coordination
 
(8) Allergy to creatine or curcumin
 
(9) With a history of drug abuse
 
(10) Doctors or researchers deem unsuitable for study participation

Treatment	
1. Patients were enrolled for baseline investigation:
 
(1) Disease status: disease stage, complications, treatment, treatment stage, drug


plan
	
use.
 
(2) General investigation: dietary investigation, digestive tract symptoms, height, weight.
 
(3) Nutritional assessment: NRS2002 and PG-SGA scores, grip strength, body composition, grip strength, deltoid skin fold thickness, upper arm muscle circumference.
 
(4) Examination and examination: blood routine, biochemical set, IL-6, TNF-α, lactic acid, serum insulin, prealbumin, transferrin, chest, and abdominal CT, PETCT, etc.
 
(5) Functional Assessment of Anorexia/Cachexia Therapy (FAACT);
 
(6) QoL Evaluation Scale: ADL scale.
 
After informed consent, patients were divided into groups A and B according to their wishes.
 
Group A: According to the national industry health standard "Dietary Guidance for Patients with Malignant Tumors 2017", basic nutrition treatment, energy 30 ~ 35kcal/kg, protein 1.0-2.0g/kg, diet deficiency, total nutrition and/or whey protein oral nutrition supplement or tube feeding enteral nutrition.
 
Group B: Since basic nutrition in group A, creatine 5g/d and curcumin 4g/d were added orally for one month.
 
2. follow-up
 
Weekly telephone follow-up, 2 weeks of routine outpatient follow-up, general condition survey, nutritional intake, nutritional assessment, routine examination, anorexia/fluid therapy functional assessment, QoL rating scale, 4 weeks of effectiveness evaluation, 3 months of survival survey.

Evaluation of curative effect
	
Efficacy evaluation indicators (primary efficacy indicators and secondary efficacy indicators)
 
Main research Indicators
 
(1) Nutritional serum indexes: blood routine, biochemical complete set, prealbumin, transferrin
 
(2) Body composition index: skeletal muscle index and body composition in L3 section of CT scan
 
(3) Inflammatory metabolism indicators: serum insulin, IL-6, TNF-α, lactic acid, PETCT to evaluate the metabolism
 
Secondary study indicators
 
(1) Physical measurements: body weight, grip strength, triceps skin fold thickness, upper arm circumference diameter
 
(2) Nutritional assessment: energy and protein intake, PG-SGA score
 
(3) Functional Assessment of Anorexia/Cachexia Therapy (FAACT)

	
(4) QoL evaluation scale: ADL score
 
(5) Survival time survey: 1, 3 months survival rate
 
(6) Evaluation of tumor efficacy: Compared with the baseline at the time of enrollment, tumor remission and progression were compared

	
Safety evaluation index
 
Creatine and curcumin taken orally by the patients in this study were both food grade: creatine is a sports nutrition food at home and abroad, which can increase muscle synthesis; Curcumin is the main component of curry, often used as a food additive, there are a variety of health food sales of curcumin abroad. After large dose of creatine supplementation (more than 25g/ day), muscle stiffness, spasm and other adverse phenomena may occur; Large doses of curcumin supplementation may cause nausea and even vomiting and diarrhea, with no toxic effects below 8g daily.
 
Both creatine and curcumin have been used orally in cancer patients in domestic and foreign studies without adverse reactions reported. The creatine (5g/ day) and curcumin (4g/ day) consumed in this study belong to the safe dosage range according to the oral dosage in domestic and foreign literatures and the dosage in the product instructions, so there are generally no side effects. For safety reasons, researchers are still closely monitoring patients for possible side effects.

Method of statistics	
Statistical analysis was performed using GraphPad Prism version 18.0 (La Jolla, CA, USA). Student's t-test was used for comparison between groups, and one-way analysis of variance (ANOVA) was used for other data. All data are presented as mean \pm SEM. $p < 0.05$(*) indicates statistical significance. $p < 0.01$(**) indicates that the difference is more statistically significant.

Duration of study	
Jun 1,2023 to Dec 31,2025

1. Background

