1.2.2 New progress in the treatment of cachexia

At present, the most studied intervention measures for cachexia include nutrition intervention, drug intervention, exercise intervention and multidisciplinary intervention mode. For the treatment of tumor-related cachexia in clinical trials [15], it has been found that many drugs may be effective against the cachexia, and these drugs basically have the following three functions [1]: reducing tumor-related inflammation; Harnessing the body's anabolic potential to combat consumption and hypercatabolic states; Stimulate appetite. However, the clinical effect of drug therapy is not stable, the individual difference is large, and the side effects are many.

Exercise has anti-inflammatory properties, which can fight the muscle degradation and insulin resistance caused by inflammation. Animal studies have shown that exercise influences reducing skeletal muscle degradation and body weight, reducing inflammation and oxidative stress, reducing depressive symptoms, and increasing anabolic hormones (such as IGF-1) [6]. However, to achieve a certain level of exercise and exercise duration, there are many uncontrollable restrictions on the implementation of exercise therapy in cancer patients.

Nutrition intervention to improve cachexia has shown its unique advantages and has been widely concerned by clinical medical staff. The basic requirement is to provide tumor patients with 30-35 kcal/kg of energy and 1.0-2.0 g/kg/day of protein. In addition, there are much research on branched chain amino acids, omega-3 unsaturated fatty acids, L-L-carnitine, and other nutrients [16]. Although nutritional support is the basic treatment for cachexia and can enable energy and protein intake to a certain extent and sustainable over a period, it does not fundamentally solve the catabolic problems. How to correct the inflammatory state and metabolic disorder of such patients, so that basic nutrition can enter anabolism, is the main problem to be solved in this study.

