Creatine is a tripeptide composed of arginine, methionine, and glycine, which can be synthesized by the body or taken from food. Creatine is a naturally occurring amino acid derivative in the human body. Creatine supplementation can improve lean body mass and muscle function, rapidly increase muscle strength, accelerate fatigue recovery, and improve explosive power. Therefore, creatine is widely used in exercise supplement and sarcopenia treatment [21]. Studies have shown that both short-term and long-term supplementation (30 g/day for 5 years) is safe and well tolerated for healthy individuals and many patients from infants to the elderly, and that low dose creatine intakes (e.g., 3 g/day) can provide

significant health benefits [21]. Many animal studies have confirmed the beneficial effect and mechanism of creatine in the cachexia of tumor [22, 23]. However, in clinical studies, the sample size is small and high-quality evidence is lacking. A randomized double-blind controlled trial in which 30 patients with stage III or IV colorectal cancer were selected to receive creatine versus placebo showed more significant improvements in phase Angle and grip strength in the creatine supplement group, but no significant effects on body composition and body weight [24]. Another study on head and neck cancer showed a significant increase in lean body mass from baseline in the creatine supplement group, but no significant difference in the control group. In addition, skeletal muscle strength was also improved in the creatine group, but there was no statistical difference between the two groups [25]. So far, there have been few relevant studies. Although the optimal creatine supplement scheme is not yet clear, it has been reported that creatine supplement of 3-5g/d can make the body reach the saturation level of creatine [9, 26]. In addition, other studies have found that creatine may enhance the invasion and metastasis of some cancers, including colorectal cancer, pancreatic cancer, and breast cancer [27], which is a problem that researchers need to pay attention to.

To sum up, although curcumin partially increases muscle mass, studies have found that curcumin is more likely to be anti-inflammatory and prevent adipose tissue decomposition, while creatine mainly improves lean body mass and muscle function. Therefore, whether the combination of the two can play a more stable synergistic effect in the treatment of cachexia is the main content of this study.

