1.3 Research to be carried out.

In this review, cachexia is a common complication of various advanced malignant tumors, which seriously affects the quality of life and survival time of patients. In view of the clinical problem of non-nutritional response in patients with cachexia, we plan to carry out a clinical case-control study on the intervention of creatine combined with curcumin in patients with cachexia. Overall, we limited the study subjects to upper digestive tract tumors and diagnosed patients with early cachexia. The main purpose of this study is to determine whether the combination of the two can play a positive and stable role in inhibiting the inflammation of cachexia and improving metabolic status, so that basic nutrition can play a role, to reduce the level of skeletal muscle consumption, maintain weight, improve quality of

life, save medical costs, and extend survival time.

2. Purpose of the study

(1) To investigate whether creatine combined with curcumin can improve the inflammatory state, correct the disorder of nutrient metabolism and improve the nutritional status in the early cachexia stage of upper gastrointestinal neoplasms.

(2) To investigate whether creatine combined with curcumin can improve the quality of life and prognosis of patients with early cachexia in upper digestive tract tumors.

3. Study design type, principle, and test procedure

(1) Study Design

Type of study design: prospective open controlled clinical trial; Non-random grouping method: According to the exclusion criteria, patients were included into group A or group B according to their wishes after informed consent; Blind level: This experiment is an open study without blind or emergency letters. Research Center: None.

Group A: basic nutrition treatment, energy 30-35 kcal/kg, protein 1.0-2.0 g/kg, diet deficiency, total nutrition and/or whey protein oral nutrition supplement or tube feeding enteral nutrition supplement.

Group B: Since basic nutrition in group A, creatine 5g/d and curcumin 4g/d were orally added, and the intervention time was 1 month.

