It was assumed that after 4 weeks of oral administration of creatine + curcumin in group B, combined with the existing literature on the improvement of the quality of the bad fluid, the skeletal muscle index at L3 section of CT scan in group B was 20% higher than that in control group A, and the standard deviation was 14%. Bilateral test was required, α was 0.05, the sample ratio between the two groups was 1:1 (i.e., the number of cases in the two groups was equal), $\beta=0.2$. The degree of assurance (test efficacy) $1-\beta=80\%$ was calculated using SPSS software, then the sample size of each group was 68 cases, considering the 10% loss of follow-up rate, each group needed 76 cases, 152 patients in total.

Follow-up test item time point

Classification	Item	0	0.5m	1m	3m
Serological indicators	blood routine	√	-	√	√
	biochemical set	√	-	√	√
	prealbumin	√	-	√	√

	transferrin	√	-	√	√
Body composition index	CT scans skeletal muscle index at L3 cross section	√	-	√	√
	BIA measures muscle mass	√	-	√	√
Inflammatory metabolic indicators	Serum insulin	√	-	√	√
	IL-6	√	-	√	√
	TNF- α	√	-	√	√
	lactic acid	√	-	√	√
	PETCT (SUV)	p.r	-	p.r	-
Physical measurements	Weight	√	√	√	√
	grip strength	√	√	√	√
	skin fold thickness	√	√	√	√
	upper arm circumference	√	√	√	√
nutrition assessment	intake	√	√	√	√
	PG-SGA score	√	√	√	√
Questionnaire Survey	Functional Assessment of Anorexia/Cachexia Therapy(FAACT)	√	√	√	√
	ADL evaluation scale	√	√	√	√

4. Criteria

Inclusion Criteria:

(1) Clinical diagnosis of advanced tumors of the upper digestive tract with untreatable or postoperative recurrence of esophageal and gastric cancer III-IV

- (2) Meet the diagnostic criteria of early cachexia (anorexia and metabolic changes, involuntary body mass reduction $\leq 5\%$ within 6 months)
- (3) Radiotherapy, chemotherapy, or immunotherapy in our hospital
- (4) Understand and fill in a variety of rating scales
- (5) Informed consent, voluntary participation in this study

Exclusion Criteria:

- (1) Neoadjuvant chemotherapy patients
- (2) Intestinal obstruction or gastrointestinal bleeding
- (3) Severe heart, lung and renal insufficiency
- (4) Coagulopathy
- (5) Clinical diagnosis with diabetes and other metabolic diseases
- (6) The expected survival time is less than 1 month
- (7) With cognitive dysfunction or poor coordination
- (8) Allergy to creatine or curcumin
- (9) With a history of drug abuse
- (10) Doctors or researchers deem unsuitable for study participation

Removal Criteria:

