Group B control group: In addition to the above basic nutrition, oral creatine powder 5g qd, curcumin capsule 2g bid for one month.

The intake, complications and survival of the patients were followed up by telephone for 1 and 3 weeks, physical indicators, nutritional assessment, FAACT and QoL scale were followed up for 2 weeks in the hospital and outpatient department, and nutritional serum indicators, body composition indicators, inflammatory metabolism indicators, physical indicators, nutritional assessment were reviewed for 4 weeks. Evaluation of effect. The long-term survival, re-hospitalization and hospitalization expenses were investigated 3 months later. To evaluate the effect of creatine combined with curcumin on improving the nutritional status, metabolic level and clinical prognosis of alimentary tract neoplasm. Note: Weight is calculated by standard weight: Standard weight (kg) = height (cm)-105.

(3) Combination of drugs

During the study period, patients may have been treated with chemotherapy drugs and immunotherapy drugs due to tumor treatment and may have taken megestrol orally against the oxalic fluid to improve appetite. To avoid the influence of the two groups of therapeutic drugs, the diseases, and drugs of the two groups will eventually be grouped and stratified to eliminate the interference of combined drug use.

(4) Safety evaluation index

- ① Incidence and severity of side effects
- ② The rate of unplanned rehospitalization.

6. Observation of adverse events

Adverse Event (Adverse Event): An adverse medical event occurs after a patient or clinical trial subject receives a drug or a formula for a special medical use, but there is not necessarily a causal relationship.

Serious Adverse Event: An event occurs during the clinical trial that requires hospitalization, prolongates the hospital stay, causes disability, affects the ability to work, threatens life or death, or

results in congenital malformations.

Adverse reaction: an adverse reaction that is harmful rather than expected but is causally related to the application of a drug or special medical use formula food during normal application of the drug or special medical use formula food at prescribed doses. In clinical trials for a new use, all reactions that are harmful and not causally related to the use of a drug or a formula for special medical use, as expected, should be considered adverse when the dose has not been determined.

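### Physical activity, which the protocol names as acting on muscle, inflammation and insulin resistance, is not among the listed items, so in self-chosen groups a baseline difference could be neither shown nor directly adjusted for

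*Combined protocol and SAP*

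**What the plan says.** Section 1.2.2 states: "Exercise has anti-inflammatory properties, which can fight the muscle degradation and insulin resistance caused by inflammation". It continues: "Animal studies have shown that exercise influences reducing skeletal muscle degradation and body weight, reducing inflammation and oxidative stress". The Summary's main indicators include the L3 skeletal muscle index, IL-6, TNF-α and serum insulin, so the text links exercise to the quantities on which the trial will be judged.

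Section 3(1) describes allocation: "patients were included into group A or group B according to their wishes after informed consent". On blinding it says: "This experiment is an open study without blind or emergency letters".

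Under Treatment plan, the Summary's general baseline item is "General investigation: dietary investigation, digestive tract symptoms, height, weight". The other baseline items cover disease status, nutritional assessment, laboratory tests and imaging, FAACT and ADL. The follow-up table in section 3 lists laboratory, body composition, physical measurement, intake and questionnaire items. The nearest to activity are grip strength and the "ADL evaluation scale". The telephone calls in section 5(2) cover intake, complications and survival.

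For confounding, section 5(3) says that "the diseases, and drugs of the two groups will eventually be grouped and stratified". Section 9 specifies a Student's t-test between groups and ANOVA for other data, and names no covariate.

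**The concern.** Under randomisation, a cause of the outcome that nobody measures is balanced on average, and the test's error rate allows for chance imbalance. Under patient choice there is no such protection. The usual safeguard is to record the known causes of the outcome at entry, compare the groups on them and adjust. The protocol names one such cause in its own background and does not list it for collection.

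If activity differed between A and B at entry, part of any difference in muscle or inflammation could come from activity and be reported as an effect of creatine plus curcumin. If the less active patients chose B, a real effect could be hidden. Readers could not tell, because there would be no activity data to tabulate. Baseline activity can be asked properly only at enrolment; a patient's later recollection is a poor substitute.

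**Working it through.** **Is activity recorded anywhere?**

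| Place | Content | Activity item |
|---|---|---|
| Summary, baseline items | Disease, diet, symptoms, height and weight, nutritional assessment, laboratory and imaging, FAACT, ADL | None |
| Section 3, follow-up table (0, 0.5, 1, 3 months) | Laboratory, CT and BIA muscle, physical measurements, intake, PG-SGA, FAACT, ADL | None |
| Section 5(2), telephone calls | Intake, complications, survival | None |
| Section 5(3), stratification | Diseases and drugs | None |
| Section 7(4), monitoring | Nutrient intake and the patient's condition | None |

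Diet is prescribed to a common standard in both groups and recorded. Activity is neither standardised nor recorded.

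**The plan's own figures.** Section 3 gives 68 per group, an SD of 14% and an assumed difference of 20%. The loss step reproduces: 68 / 0.9 = 75.6, so 76 per group and 152 in total. The 68 does not follow from 20% and 14%: 2 × (1.960 + 0.842)² × (14/20)² = 7.7, so 8 per group (9 with the t distribution). That is a separate matter. Here 68 serves only as the planned number analysed.

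**How large could the bias be?** The documents give neither the share of active patients nor the size of an activity effect. Both are assumed:

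- g, the shift in an outcome due to activity: 0.25 to 0.5 SD.
- D, the difference between B and A in the share of active patients: 10 to 40 percentage points.
- No true supplement effect, 68 per group, two-sided 5% t-test with 134 degrees of freedom.

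Formulas: bias in SD units = D × g. Bias in L3 points = bias × 14, taking the 14% as the SD on the same scale as the 20% difference. Noncentrality = bias × √(68/2) = bias × 5.83. The rejection rate comes from the noncentral t distribution.

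| D | g (SD) | Bias (SD) | L3 points | Rejection rate |
|---|---|---|---|---|
| 10 points | 0.25 | 0.025 | 0.35 | 5.2% |
| 10 points | 0.5 | 0.05 | 0.7 | 6.0% |
| 20 points | 0.25 | 0.05 | 0.7 | 6.0% |
| 20 points | 0.5 | 0.10 | 1.4 | 8.9% |
| 30 points | 0.25 | 0.075 | 1.05 | 7.2% |
| 30 points | 0.5 | 0.15 | 2.1 | 14.0% |
| 40 points | 0.25 | 0.10 | 1.4 | 8.9% |
| 40 points | 0.5 | 0.20 | 2.8 | 21.2% |

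The rates are the same, in the opposite direction, if group A is the more active.

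For scale, 68 per group at an SD of 14% detects about 6.8 points (0.48 SD) with 80% power. The largest bias in the table, 2.8 points, is 41% of that and 14% of the assumed 20% difference.

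The table describes an unadjusted comparison. Adjustment for baseline values related to activity would lower these figures by an amount the documents do not allow one to compute.

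**The case against.** **The imbalance is conjecture.** This stands. Section 1.2.3 notes that "creatine is widely used in exercise supplement and sarcopenia treatment", and the Summary calls creatine a sports nutrition food. A reader might infer that active patients will prefer group B. The documents do not support that: these are product descriptions and background, nothing shows that patients choose on them, the consent text is not available, and group B also takes curcumin. Frailer patients could equally prefer B.

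**Section 1.2.2 is weaker than the quoted sentence suggests.** This stands in part. Some of its support is animal data, and it adds that exercise therapy is hard to deliver in cancer patients. These patients have advanced disease and are under treatment, so large shares of vigorous exercisers are unlikely. But the caveat concerns therapeutic exercise and does not show that everyday activity is uniform.

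**Baseline values already collected would do the work.** This stands in part. A reader might infer that without an activity item no later analysis could correct for activity at all. That is too strong. L3 index, BIA muscle mass, IL-6, TNF-α, insulin, grip strength and ADL are all taken at time 0. Habitual activity would act partly through them, and adjusting for baseline values does not remove a supplement effect. None is described as a measure of activity, however, and section 9 specifies no adjusted model. The Summary also mentions a survey of general condition at follow-up, without listing its items.

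**Activity may rise because of the supplements.** This stands. Such a rise may be part of the treatment's effect rather than confounding, so the point is confined to activity at entry.

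**The root problem is allocation by choice.** True, and an activity item does not cure it. While allocation stays as it is, a cause that the protocol names is a reasonable one to measure.

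**Conclusion.** The point holds as a gap in data collection. With self-chosen, open groups, a baseline difference in physical activity could be neither shown nor directly adjusted for, although the protocol names exercise as acting on the processes its main indicators reflect. Adjustment for the baseline outcome, grip strength and ADL would remove part of such a difference.

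It is not evidence of bias. A reader might infer that a favourable result for group B would be due to exercise. The documents show neither that activity differs between the groups nor in which direction. Under the assumed values the bias is about 0.03 to 0.20 SD, and the rejection rate about 5% to 21%. A 10-point imbalance is close to negligible (5% to 6%), and 21% needs both assumptions at their upper ends. This is a cheap improvement to make, subordinate to the lack of randomisation.

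**What to change.** 1. Add one short self-reported item, such as days and minutes of exercise in the past week, to the baseline list in the Summary and to the 0, 0.5, 1 and 3 month columns of the follow-up table, asked identically in both groups.
2. In section 9, specify that the A versus B comparison includes baseline activity and the baseline value of the outcome as covariates.
3. Tabulate baseline activity by group. Report follow-up activity by group descriptively, and do not adjust for it, since the supplements may change it.

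The cost is about one minute per existing visit and the added covariates, with no extra visit or procedure and no change in sample size. If enrolment has begun, patients already entered will lack the baseline value, and the report should say how many. Self-report is imprecise, and confounding by activity and by other unmeasured differences will remain. Only randomisation would remove it.

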The clinical study will develop a data safety monitoring plan according to the risk. All adverse events are recorded in detail, properly handled and tracked until properly resolved or the condition is stable, and serious adverse events and unexpected events are reported to the Ethics Committee, competent authorities, sponsors and drug regulatory authorities in a timely manner in accordance with regulations; The principal investigator conducts regular cumulative reviews of all adverse events and holds investigator meetings where necessary to assess study risks and benefits; For studies with greater than minimum risk, an independent data monitor will be assigned to monitor the study data. For high-risk studies, an independent Data Safety Monitoring committee will be established to monitor the accumulated safety and efficacy data and make recommendations on whether to proceed.

9. Statistical analysis

Statistical analysis was performed using GraphPad Prism version 8.0 (La Jolla, CA, USA). Student's t-test was used for comparison between groups, and one-way analysis of variance (ANOVA) was used for other data. All data are presented as mean \pm SEM. $p < 0.05$ (*) indicates statistical significance. $p < 0.01$ (**) indicates that the difference is more statistically significant.

10. The ethics of clinical research

Clinical research will follow the relevant regulations such as the Declaration of Helsinki of the World Medical Congress. Clinical studies are conducted only after the protocol is approved by the Ethics Committee prior to the start of the study. Before each subject is enrolled in this study, the investigator is responsible to give a complete and comprehensive introduction of the purpose, procedure and possible risks of this study to the subject or his/her agent and sign a written informed consent. Subjects should be informed that they have the right to withdraw from this study at any time, and informed consent should be kept as a clinical study document for future reference. Subjects' privacy and data confidentiality will be protected during the study.

11. Research schedule

Jun 1,2023 to Aug 31,2023: The formal implementation of the project was started. 76 cases were collected, and baseline investigation was conducted for enrolled patients. The patients were not randomly enrolled, and grouped intervention was performed.

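### The Summary names the skinfold site and the arm measure differently at baseline and as secondary endpoints, so a like-for-like baseline is not assured (minor)

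*Combined protocol and SAP*

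**What the plan says.** Three places in the combined protocol and SAP name the arm measures.

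- **Summary, Treatment plan, baseline item (3), nutritional assessment:** "deltoid skin fold thickness, upper arm muscle circumference".
- **Summary, Evaluation of curative effect, secondary indicator (1):** "Physical measurements: body weight, grip strength, triceps skin fold thickness, upper arm circumference diameter".
- **Section 3, follow-up schedule table:** one row for "skin fold thickness" and one for "upper arm circumference", each ticked at 0, 0.5, 1 and 3 months.

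Section 5(2) does not itemise the measures. It says that "physical indicators, nutritional assessment, FAACT and QoL scale were followed up for 2 weeks in the hospital and outpatient department". No section describes how the arm is measured, and none gives a formula for muscle circumference. The analysis, in the Summary and in Section 9, is one general sentence: "Student's t-test was used for comparison between groups, and one-way analysis of variance (ANOVA) was used for other data". It does not say whether these measures are analysed as follow-up values or as change from baseline.

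**The concern.** Deltoid and triceps are different skinfold sites. Upper arm muscle circumference is a derived quantity, while upper arm circumference is read directly from a tape. A circumference and a diameter are also not the same thing, so the endpoint wording does not identify one measure. Someone completing the case report form from the baseline list could record a different pair of quantities from someone working from the endpoint list.

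What is at stake is the baseline. Patients join group A or B according to their own wishes (Summary; Section 3), so nothing in the design balances arm size or fat at the start. A baseline value of the same quantity as the endpoint is needed to see whether the groups began alike and to adjust if they did not. Section 1.1 also frames the aim as losing less muscle and weight, which is a question about change within patients.

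**Working it through.** The plan states no figure on this point, so there is none to reproduce. The check is a comparison of texts, followed by an illustration.

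**Step 1. The texts side by side**

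| Place | Skinfold | Arm measure | Times |
|---|---|---|---|
| Summary, baseline list | deltoid | muscle circumference | baseline |
| Summary, secondary indicators | triceps | circumference, with diameter added | none given for these items |
| Section 3, schedule | site not named | circumference | 0, 0.5, 1, 3 months |

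The two Summary lists disagree on both items. The schedule resolves part of this: one skinfold item and one arm item are planned at baseline and repeated at each later visit. It does not resolve the skinfold site. Its arm label agrees with the endpoint list rather than the baseline list.

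**Step 2. How far apart the two arm quantities are**

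The documents give no arm measurements and no formula. The following therefore rests on the usual definition and on assumed values.

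Formula: AMC = MAC - π × TSF, where AMC is arm muscle circumference, MAC is arm circumference and TSF is triceps skinfold, all in cm.

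Assumed ranges: MAC 24-30 cm, TSF 0.8-1.8 cm (8-18 mm).

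- Middle case, MAC 27 and TSF 1.2: π × 1.2 = 3.77; AMC = 27 - 3.77 = 23.23 cm; 3.77 / 23.23 = 16.2%.
- Smallest gap, MAC 30 and TSF 0.8: π × 0.8 = 2.51; AMC = 27.49 cm; 2.51 / 27.49 = 9.1%.
- Largest gap, MAC 24 and TSF 1.8: π × 1.8 = 5.65; AMC = 18.35 cm; 5.65 / 18.35 = 30.8%.

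Recording AMC at baseline and MAC later would therefore show an apparent gain of 9-31% in an arm that had not changed. That happens only if the two quantities are mixed in this way, which the schedule does not plan.

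**Step 3. Would such a mix-up cancel between the groups?**

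Apparent change = MAC(follow-up) - AMC(baseline) = true change in MAC + π × TSF(baseline).

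The extra term cancels between groups only if their mean baseline triceps folds are equal. For each 1 mm by which those means differ, π × 0.1 cm = 0.31 cm remains in the group contrast. Self-chosen groups give no assurance of equality, and a deltoid fold would not supply the value needed to check it.

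**The case against.** The strongest reply is that this is a labelling slip and nothing more. The only visit-by-visit table has a single row for each item, ticked at time 0 and at every later visit, so like-for-like values are planned. The endpoint list is a list of outcomes; it does not instruct anyone to take different measures after baseline. The English is loose elsewhere, and the same baseline line lists grip strength twice. The planned test is a comparison between groups, so a mislabelled baseline would leave the follow-up comparison intact. The muscle question rests mainly on the CT skeletal muscle index at L3, which is a main indicator and the basis of the sample size, supported by muscle mass from BIA.

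Most of this stands. In particular, a reader might infer that baseline and follow-up are different quantities, so that change in these measures has no meaning. The documents do not support that: the schedule points to the same item throughout, and no change score is defined for these measures. Nor do they support treating raw arm circumference as a failure of the trial's muscle assessment, given the CT and BIA measures.

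Two things remain. The schedule does not name the skinfold site, and no procedure elsewhere supplies it. And although a between-group test at follow-up could still be computed, with self-chosen groups it cannot separate treatment from starting differences unless a matching baseline exists.

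**Conclusion.** The plan is wrong as written, but the point is minor. The Summary contradicts itself on the skinfold site and on the arm measure, and no other section settles either. Loose naming or translation is a plausible explanation that the documents cannot confirm. If the lists were followed literally, the baseline would not match the endpoint, and the means to check or adjust for differences between self-chosen groups on these measures would be lost.

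The effect is confined to two items filed under "Secondary study indicators"; the CT-based muscle endpoint and the sample size are untouched. The 9-31% gap depends on the assumed arm and skinfold values and on one particular mix-up. It shows why the names matter and does not predict what will happen.

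**What to change.** 1. In the baseline list, the secondary endpoint list and the schedule table, use identical wording: triceps skinfold and mid-upper-arm circumference, on the same arm, at 0, 0.5, 1 and 3 months. Delete the words deltoid and diameter.
2. Add a derived measure at every visit: arm muscle circumference (cm) = mid-upper-arm circumference (cm) - 3.14 × triceps skinfold (cm). Report it as a supportive secondary measure alongside raw circumference.
3. In Section 9, state whether the follow-up value or the change from baseline is analysed for these measures, and compare the groups with the matching baseline value taken into account, for example as a covariate. This adjusts only for the measured starting value; it does not remove other differences that come with self-chosen groups.

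The cost is wording in three places and on the case report form, one formula, and a sentence in Section 9. No extra measurement is needed, because a skinfold and an arm circumference are already scheduled at every visit. If enrolment has begun, check which site and which arm quantity were actually recorded before pooling those data with later ones.
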